#### PROTOCOL Biomedical Research Saint Louis University

Protocol Title:

SURGX antimicrobial gel versus povidone-iodine skin incision prep for the prevention of bacterial seeding in total shoulder arthroplasty

Note, if all relevant plan information is included in DSMB question above, select 'Yes' and state "see above" in the answer box.

\_\_\_\_\_

If yes, provide details (labeled a-e) including: a) what types of data or events are captured and how are they documented, b) who is monitoring data, their independence/affiliation with the research and their degrees/qualifications, c) frequency of aggregate data review, d) who is reviewing SAEs in real time (MD or DO), and e) stopping/halting rules (if any exist).

a) Outcome and adverse event data will be collected by the research team and documented electronically. Any AEs/SAEs observed will be collected on the date of the patient's surgery by the research team and reported to the PI. This would include any reaction to the application of the product such as skin irritation, rash, or burning. This would be treated at the time of surgery with irrigation of the wound to flush the area and dilute the product. If a severe case were to happen then steroid medication would be administered. There are no follow up appointments or study procedures after the date of surgery included in the research study. AEs or SAEs will be recorded in a spreadsheet with severity and causality noted. The spreadsheet will be kept on a SLU-managed computer with encryption.

b) The data will be monitored by the PI and study team members. The PI, [name], is an orthopaedic surgeon familiar with the use of the products in the study. He also has 15+ years of research experience. Other qualified team members include: [name], orthopaedic surgeon with years of research experience, [name], orthopaedic surgery resident, and [name], orthopaedic surgery resident.

c) Aggregate data will be reviewed after the first 20 participants have completed the study to detect benefit, harm, or futility of the interventions in addition to any AE or SAE trends. Following this initial review, the data will be analyzed every three months if the study continues longer than the expected time frame of 3-4 months.

d) SAEs will be reviewed in real time by the PI (MD). The PI will ensure appropriate classification of the event.

e) Because the study interventions are not considered outside the standard treatment, we do not anticipate the need for stopping/halting rules that would differ from standard treatment of a patient undergoing surgery.

If no, please justify why not.

- 12. In case of international research (research outside of the U.S. or research on international populations (non-U.S.)), describe qualifications/preparations that enable you to evaluate cultural appropriateness and estimate/minimize risks to subjects. Include whether research is sensitive given cultural norms.
- a. State any local laws/regulations governing Human Subjects Research in the country(ies) you will conduct the research and attach any relevant approvals. If none, state N/A.

e-Protocol PROTOCOL Protocol # 32325 [name] **Biomedical Research** Saint Louis University Protocol Title: SURGX antimicrobial gel versus povidone-iodine skin incision prep for the prevention of bacterial seeding in total shoulder arthroplasty \_\_\_\_\_ Will there be language barriers and if so, how will they be addressed? b. Note: If materials are to be distributed to subjects in their native language, please follow SLU's Guidance For Studies Involving Non-English Speaking Subjects. technical information and data, as well as information has international components, contact the SLU Export control policies apply. \_\_\_\_\_ \* \* \* Benefits/Alternatives. Procedures to Maintain Confidentiality and Privacy \* \* \* 10. Benefits/Alternatives Benefits. Describe the potential benefit(s) to be gained by the subjects and how the results of the study a) may benefit future subjects and/or society in general. Indicate if there is no direct benefit to the participants. It is known that bacteria (Cutibacterium acnes) is present in up to 73% of cases after shoulder arthroplasty is performed. It is not known if this bacteria will increase the risk of infection late term. The goal of this study is to see if this bacterial presence can be reduced by prepping the skin incision after it has been made. The potential benefit is that if the bacterial presence is reduced or eliminated by prepping the skin incision (for those subjects in treatment groups), the potential development of late term infection may be reduced. An individual subject may or may not benefit from participation in the study. Society may benefit from the potential knowledge gained regarding skin incision preparation as a result of this study, improving practices for patients undergoing shoulder arthroplasty. Alternatives. Describe any alternative treatments and procedures available to the subjects should they b) choose not to participate in the study. If no such alternatives exist, please state that the alternative is nonparticipation. For some studies, such as record reviews, a description of alternatives would not be applicable. There is no standard skin preparation, the alternative would be nonparticipation. Of note, povidone-iodine and SurgX gel are available for all patients and is stocked on the shelf at the hospital. 11. Procedures to Maintain Confidentiality and Privacy Federal regulations require that research materials be kept for a minimum of three (3) years and HIPAA documents be kept for a minimum of six (6) years after the closure of the study. For FDA-regulated or sponsored projects, the PI may be required to keep the data and documents for a longer time period. Confidentiality

To determine whether adequate provisions for confidentiality of data are in place, the IRB must ensure that

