There is no standard of care in regards to skin/dermis preparation for shoulder arthroplasty at SLU or in the field of shoulder replacement surgery. Common skin/dermis preparations include preoperative skin cleansers, betadine preparation, chlorhexidine skin preparation, and intraoperative irrigation with various solutions. All patients will receive standard pre-operative prophylactic antibiotics. They will all receive the same preoperative skin preparation with Hibiclens (chlorhexadine) and ChloraPrep (2% chlorhexadine gluconate / 70% isopropyl alcohol solution) prior to draping. Intra-operative irrigation will be standardized with Irrisept (chlorhexidine gluconate 0.05% in sterile water). During the study, the control group will not receive a skin incision prep after the incision is made while the other treatment groups will receive either povidone-iodine skin incision prep or SurgX gel prep. We are only looking for the presence of bacteria at the conclusion of the study. It is not known if this bacteria is clinically important but if present could potentially present as a late term infection. These infections may not present themselves for 2-10 years postoperatively. The assessment in this study is to see if this bacterial presence can be reduced after shoulder arthroplasty with the theoretical potential advantage of reducing late term infections. Patients will have standard of care follow up appointments with their physician which are typically at 2-weeks, 6-weeks, 3 months, 6 months, and yearly (no end date) following shoulder arthroplasty. These are not part of the research study.

g) Does this study involve any diagnostic imaging, labwork or genetic testing that could Y result in clinical discovery (diagnoses, genetic mutations, etc.)? Note that this could include discovery that is expected (related to the research) or incidental (not related to research aims, but possible, like a mass/shadow found in imaging despite not looking for it).

If yes, please describe and include whether there are plans to share findings with study participants.

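### Adverse events are collected on the day of surgery, so a non-serious skin or wound reaction first noted at the routine 2-week visit has no shown route into the promised harm review

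*Combined protocol and SAP*

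**What the plan says.** In the Data Safety Monitoring Plan (section 9, item 11):

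- **Item a.** "Any AEs/SAEs observed will be collected on the date of the" patient's surgery, by the research team, who report them to the principal investigator. "This would include any reaction to the application of the product such as skin irritation, rash, or burning". Events go into a spreadsheet with severity and causality. The item also states: "There are no follow up appointments or study procedures after the date of surgery included in the research study".
- **Item c.** Aggregate data are reviewed once the first 20 participants have completed the study, "to detect benefit, harm, or futility of the interventions in addition to any AE or SAE trends". Three-monthly reviews follow only "if the study continues longer than the expected time frame of 3-4 months".
- **Item d.** The principal investigator reviews serious events in real time. No end date is given.

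Elsewhere:

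- **Section 3f** lists the usual visits, starting at 2 and 6 weeks, and says: "These are not part of the research study".
- **Section 9, items 3 and 4** list local skin effects for povidone-iodine and for the gel, without onset times.
- **Section 3b** says that medical-record information will be collected according to the data collection sheet. It does not mention adverse events or a time window.
- **Section 16** lists that data collection sheet and a 2024 safety (DSM) file. Their content is not reproduced.

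**The concern.** The plan names the reactions that it wants recorded and promises to look for harm. It then ties collection to a single day and sets aside the first occasion on which a clinician would normally look at the wound again. If item a is followed as written, the review in item c and any safety sentence in the report describe the day of surgery. A reader could take "no reactions recorded" to mean that the skin and wound were uneventful through early healing, which the described collection would not have observed.

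The stake is the meaning of the safety statements. The culture comparison does not depend on it, and the plan claims no comparative safety endpoint.

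**Working it through.** The plan gives no adverse-event rate or safety sample size to reproduce. The check is therefore of the text, followed by short arithmetic on timing and precision.

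**1. Is there a route for a reaction first seen at 2 weeks?**

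| Possible route | What it provides |
|---|---|
| Item a | Collection on the date of surgery; later appointments outside the research |
| Section 3f | Routine visits exist, but are outside the research |
| Item c | A review; it names no source of later events |
| Item d | Serious events only; no time limit, so later ones may be covered |
| Section 3b, medical records | Depends on the data collection sheet (not shown) |
| 2024 DSM file | Not shown |

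The gap that remains is for non-serious reactions, subject to the last two rows.

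**2. Would a 2-week note be available at the first review?** Assume even accrual of 60 patients and 1 month = 4.348 weeks.

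- Section 3b (2–3 months including 2-week cultures): accrual lasts 2 × 4.348 − 2 = 6.70 to 3 × 4.348 − 2 = 11.04 weeks. The rate is 60/6.70 = 8.96 to 60/11.04 = 5.43 patients per week.
- Section 8k (3–4 months, taken as accrual alone): 13.04 to 17.39 weeks, or 4.60 to 3.45 per week.

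The answer depends on what "completed" means in item c, which is not defined:

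- Two-week cultures final: all of the first 20 are at least 2 weeks from surgery, by definition.
- Operated on: 20 − 2 × rate = 2.1, 9.1, 10.8 and 13.1 patients at the four rates, so about 2 to 13 of 20.
- Cultures final, but clinic visits one week late (assumption): 20 − rate = 11.0, 14.6, 15.4 and 16.6, so about 11 to 17 of 20 have a note.

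**3. Time cost.**

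- *Two-week note.* It falls due about when the last cultures become final. On the section 8k timeline that is 3–4 months + 2/4.348 = 3.46–4.46 months. With the stated month of analysis it is 4.46–5.46, inside the stated 6 months.
- *Six-week note.* On the same timeline, 3–4 months + 6/4.348 = 4.38–5.38 months. With one month of analysis it is 5.38–6.38, which passes 6 months at the upper end. On the section 3b timeline the notes close at 2.92–3.92 months, and with analysis at 3.92–4.92.

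**4. What could the review show by arm?** Alternation (section 2c) over IDs 1–20 gives control 1, 4, …, 19 = 7; povidone-iodine 2, 5, …, 20 = 7; gel 3, 6, …, 18 = 6. With no events, the exact two-sided 95% upper limit is 1 − 0.025^(1/n):

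- n = 7: 41.0%
- n = 6: 45.9%
- n = 20 (end of study, every patient with a note): 16.8%

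**5. Number of look-ups.** 3 groups × 20 patients × 1 visit = 60.

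**The case against.** The strongest reply has five parts.

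- **The likely home of the answer is unseen.** Section 3b points to the data collection sheet, and a DSM file was attached in 2024. Either could provide later capture. This stands, and limits the point to what is shown. A reader might infer that the study has no process for postoperative events; the documents do not support that.
- **Item a is not fully closed.** It does not say "only", its opening sentence and its spreadsheet sentence carry no date, and item d has no time limit. A reader might infer that serious events after the day of surgery are lost; that does not follow. Collection limited to the day of surgery is the natural reading of item a, but it is a reading.
- **The surgeons probably see these patients anyway.** Participants are recruited from the surgeons' own patients, and two orthopaedic surgeons monitor the data. If they are the same people (an inference, since names are removed), they would see late reactions in clinic. That lowers the practical stakes but creates no written route into the record.
- **Low risk justifies light monitoring.** The listed effects are mostly temporary irritation, burning and stinging. The more severe povidone-iodine effects appear tied to serious iodine allergy, which is an exclusion. This supports having no monitoring board and no special stopping rules, which is how the plan uses it. It does not say what period the harm review covers.
- **The loss cannot be measured.** This is correct. A reader might count the uncovered calendar days and infer that most reactions are missed. Days are not risk, and the documents give no onset times or rates.

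**Conclusion.** The point holds as a cheap improvement. As shown, a non-serious skin or wound reaction first noted at the usual 2-week visit has no route into the adverse-event spreadsheet, although item c promises a review for harm and trends.

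Its size is modest and cannot be expressed as a number of missed events. Even with complete capture, precision by arm is very low: upper limits of 41% to 46% for zero events at the first review, and 16.8% at the end. The gain is therefore an accurate description of what was observed, not a powered safety comparison.

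The conclusion rests on two conditions: that item a means what it most naturally says, and that neither the data collection sheet nor the 2024 DSM file already provides postoperative capture. If either does, only item a's wording needs aligning with it. The timing figures also assume even accrual on the stated timelines.

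**What to change.** 1. **Item a.** State that adverse events, serious or not, are collected on the date of surgery and, by chart abstraction done the same way in all three groups, from the routine visit nearest 2 weeks. State that no research visit is added.
2. **Data collection sheet.** Add visit date or not attended; skin or wound reaction (yes, no, not documented); onset; severity; causality. Word the reaction field without reference to a product, since the control group receives none.
3. **Item c.** Define "completed" as 2-week cultures final and the 2-week note either checked or recorded as unavailable. This also deals with late visits.
4. **Report.** Describe events by arm among patients with a note at that visit, and state the window covered.

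**Cost.** At most 60 chart look-ups by the existing team. Some notes will be missing or thin. Abstraction is not stated to be blinded, as section 2c blinds patients only, and the report should say so. A data-sheet, consent or HIPAA update may be needed: in section 15, question 3, hospital and medical records are ticked but physician/clinic records are not.

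**Optional.** A 6-week abstraction could be added, but on the section 8k timeline it may push the study past the stated 6 months.

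**Minimum alternative.** If the 2-week check is not adopted, state in items a and c, and in any report, that the harm review and safety statements cover the day of surgery only.

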#### PROTOCOL Biomedical Research Saint Louis University

Protocol Title:

SURGX antimicrobial gel versus povidone-iodine skin incision prep for the prevention of bacterial seeding in total shoulder arthroplasty

research materials are stored in appropriate locations throughout the study (during collection, transport/transmission, analysis and long term storage). Research information must be protected using appropriate safeguards based on identifiability of the data and risk associated with the study (See SLU IRB Confidentiality Guidelines).

\_\_\_\_\_

For the questions below, please use the following definitions:

Anonymous/De-identified: data contain no identifiers, including code numbers that investigators can link to individual identities;

Coded: data in which (1) identifying information, such as name or social security number, has been replaced with a number, letter, symbol, or combination thereof (i.e., the code), and (2) a key to decipher the code exists enabling linkage of data to identifying information (e.g., a master list), and (3) the key (master list) is kept separately from coded data; AND/OR

Identifiable: data that includes personal identifiers (e.g., name, social security number), such that information could be readily connected to respective individuals.

a) Electronic (Computer) Data

Click "Add" to enter data security information for each type of electronic data that will be created in the study: anonymous/de-identified, coded, and/or identifiable (see definitions above).

To properly address this question, there should only be one listing of each type of data in the table. Depending on your project, you could have up to three types of data. See the SLU ITS Sensitive Data Guide for acceptable data security methods.

Not Applicable, No Electronic (Computer) Data Study IRB-approved Prior to New Question (Question N/A- Grandfathered)

**Electronic Data** 

Type of Data	Storage Location	Data Transmission Outside of SLU	Supplemental information related to above items can be entered here or leave blank:
Coded	SLU ITS managed device (computer, tablet, etc.) with encryption	Not Applicable, I will not be sending/sharing electronic data outside of SLU	

#### b) Hardcopy (Paper) Data

#### PROTOCOL Biomedical Research Saint Louis University

Protocol Title:

SURGX antimicrobial gel versus povidone-iodine skin incision prep for the prevention of bacterial seeding in total shoulder arthroplasty

Click "Add" to enter information for each type of hardcopy (paper) data that will be created in the study: anonymous/de-identified, coded, and/or identifiable (see definitions above).

\_\_\_\_\_

To properly address this question, there should only be one listing of each type of data in the table. Depending on your project, you could have up to three types of data.

Not Applicable, No Hardcopy (Paper) Data Study IRB-approved Prior to New Question (Question N/A- Grandfathered)

#### Hardcopy Data

Type of Data	Storage Location	Transported Data Security	Supplemental information related to above items can be entered here or leave blank:
Identifiable	SLU Locked Cabinet; SLU Locked Room/Office	Personnel Supervision	Intra-operative culture specimens will be stored by a SLU laboratory until final results are obtained, then will be discarded per lab protocol. Hardcopy consents will be stored in SLU locked cabinet/room/office under personnel supervision

c) If a master list is used in this study (linking study codes to subject identifiers), explain: a) how and where you will secure the master list, b) how long it will be kept/when it will be destroyed, and c) provide a sample of the code.

a) The master list will be a separate Excel sheet stored in a SLU-managed encrypted device on a secure T drive. Only the research team will have access to the master list.

b) The list will be maintained until the study has ended and been published.

c) Participants will be coded 001, 002, 003, etc. and will be the only data sheet linked to patient identifiers. The coded data collection sheet will contain this number and no patient identifiers.

d) If data or specimens are being shared outside of the research team, indicate who will receive the material, specifically what they will receive (data or specimens), and if an agreement has been signed to cover the transfer. Note: unless covered under a Clinical Trial or other agreement, the transfer of data or specimens to an external entity will require an agreement. For the transfer of materials (specimens), a Materials Transfer Agreement (MTA) is used; for the transfer of data, a Data Use or Data Transfer Agreement is used. Please contact the Research Innovation Group at [contact] for assistance.

No data will be shared outside of the study team including with the drug/device manufacturer.

e) If samples or data will be provided to SLU from an outside source, indicate whether you will have access

C-PROTOCOL		PROTOCOL Biomedical Research Saint Louis University	Protocol # 32325 [name]
Protocol Title:		SURGX antimicrobial gel versus povidone-iodine skin incision prep bacterial seeding in total shoulder arthroplasty	for the prevention of
	to identifie agreement external er Transfer A Agreemen assistance n/a	rs, and if so, how identifiable information is protected. Note: unless covered under a (e.g., Clinical Trial Agreement or subcontract), the transfer of data or specimens fi tity to SLU may require an agreement. For the transfer of materials (specimens), a greement (MTA) may be required; for the transfer of data, a Data Use or Data Trar t may be required. Please contact the Research Innovation Group at [contact]	another rom an I Materials Isfer 7 for
f)	lf data will Describe h removed fi	be collected via e-mail or the Internet, how will anonymity or confidentiality be affect ow data will be recorded (i.e., will internet protocol (IP) addresses and/or e-mail ac om data?).	cted? dresses be
g)	If you will b images of including a archiving,	be audio/video recording or photographing subjects, provide a rationale as voicepri faces/unique body markings are considered identifiers. Describe confidentiality pro ny restricted access to images and/or the final disposition of the recordings/photos etc.).	nts and ocedures, (destruction,
h)	Describe a participant applicable Epic Rese	ny study-specific (non standard of care) information or documentation that will be p s' medical records for this research (e.g., study visit notes, lab results, etc.). If none '. NOTE: documentation of research in Epic should be done in accordance with the arch Charting Policy and Clinical Workflow: Documenting Research Encounters in Itures obtained for the study will show up as lab results in the patients' medical rec	out in the , state "not SLUCare Epic. ords
i)	Are the RFP/Av safegua If yes, s	re any information security requirements identified in the project's N vard Notice/Contract? This could include data security, technical urds, security controls, NIST, FISMA, CFR, etc. SLU ITS approval is required. Contact [contact] to start roval process.	olus.
Priv	vacy		
	Privacy ref	ers to persons having control over the sharing of oneself with others.	
j)	Please indica	te how participant privacy will be protected in this study (select all that apply):	
	Х	Discussion of health related and/or personal information in a private room/area	
	Х	Research interactions/interventions are conducted in a private room/area	
		Use of drapes or other privacy measures	
	х	Collection of sensitive/identifiable information is limited to the minimum necessary	to achieve

C-PROTOCOL
------------

